10.2.1. Within-treatment Changes

For variables measured on a continuous scale, the statistical significance of within-treatment changes between time points will be investigated using paired t-tests. For variables measured on an ordinal categorical scale, the Wilcoxon signed-rank test will be employed.

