7. SUBJECTS

7.1. *Subject Population*

Eligible test subjects will be presenting for cataract surgery who are interested in a reduced dependence on spectacles for near, intermediate, and distance vision, who have axial length $\geq 24.5\text{mm}$ in both eyes, and who are considered appropriate candidates for extended depth of focus (EDOF) lens implantation. Target refraction will be -0.25 D in all eyes.

A total of 40 eyes of 20 subjects at one site will be enrolled. Both eyes of a subject must be enrolled. Subjects must meet the inclusion criteria. Prior to enrollment, subjects will be provided information on the study and asked to sign a patient information and consent form to participate. The patient information and consent form will be approved by an appropriate ethics committee.

7.2. *Inclusion Criteria*

Subjects are eligible for the study if they meet the following criteria:

Note: Ocular criteria must be met in both eyes.

- Undergoing uncomplicated bilateral cataract surgery with IOL implantation.
- Gender: Males and Females.
- Age: 50 years or older.
- Willing and able to provide written informed consent for participation in the study.
- Willing and able to comply with scheduled visits and other study procedures.
- Motivated for greater degree of spectacle independence vs monofocal IOL.
- Axial length $\geq 24.5\text{mm}$ in both eyes.

- Planned cataract removal by femtosecond laser.

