9.5. Discontinued Subjects

Discontinued subjects are those who do not have an exit visit or who come into the office to be exited prior to the scheduled final study visit. Subjects may be discontinued from the study at any time if, in the opinion of the investigator, their continued participation in the study poses a risk to their health. The reasons for discontinuation include:

- a. Adverse event;
- b. Lost to follow-up;
- c. Subject decision unrelated to an adverse event;
- d. Protocol violation;
- e. Treatment failure;
- f. Other.

To ensure the safety of all subjects who discontinue prior to Visit 6, investigators should assess each subject and, if necessary, advise them of any therapies and/or medical procedures that might be needed to maintain their health. Any changes in medical health and/or use of concomitant medications should also be captured.

10. ANALYSIS PLAN***10.1. Analysis Data Sets***

All subjects who are enrolled in the study will be evaluated for safety. Efficacy analyses will be performed based on data from those eyes where uncomplicated cataract surgery with Vivity IOL implantation was completed.

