10.2. Statistical Methodology

A summary of the data will be prepared for all measurement time points. Summaries of the changes observed between the 1 month and 3 month post-operative visits will also be summarized.

For variables measured on a continuous scale, these summaries will include the sample size, as well as the mean, standard deviation, median, minimum, and maximum. For variables measured on a categorical scale, summaries will provide the number and percentage of subjects who provided each score (or change in scores). These summaries will be provided for all eyes completing the study.

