10.3. General Statistical Considerations

The statistical analyses will be performed using R, version 4.0.3 or higher. Any statistical tests of hypotheses will employ a level of significance of alpha=0.05.

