11. SAMPLE SIZE JUSTIFICATION

The distribution of axial length ≥ 24.5 mm in the older population of is $\sim 17\%$.³ As a result, recruitment for qualifying candidates will be limited due to this natural population distribution. It is expected that 20 patients (40 eyes) will provide sufficient data to characterize the clinical performance of the lens. When the sample size is 20, a two-sided 95% confidence interval for a single mean will extend 0.05 from the observed mean, assuming that the standard deviation is known to be 0.1 logMAR and the confidence interval is based on the t-statistic.

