15. STANDARD EVALUATION PROCEDURES

Table 15.1. Proposed Visits and Study Assessments

(visits are by patient, with both eyes tested)

Activity	Pre-operative	Operative	Postoperative			
	Visit 1	Visit 2	Visit 3	Visit 4	Visit 5	Visit 6
			1 Day	1 Week	1 Month	3 Months
Informed Consent	X					
Demographics	X					
General Information: Medical History	X					
Surgery		X				
Manifest refraction	X			X	X	X
Monocular uncorrected distance VA	X		X	X	X	X
Monocular best corrected distance VA	X			X	X	X
Monocular uncorrected and best distance-corrected intermediate VA				X	X	X
Monocular uncorrected and best distance-corrected near VA				X	X	X
Binocular uncorrected and best-corrected distance VA						X
Binocular uncorrected and best distance-corrected intermediate VA						X
Binocular uncorrected and best distance-corrected near VA						X
Binocular distance corrected low contrast VA						X
IOLSAT Patient Satisfaction Survey						X
QUVID Visual Disturbance questionnaire						X
Monitor for Adverse Events and Device Deficiencies		X	X	X	X	X
Complete Exit Form ¹						X

¹ Complete Exit Form upon termination of subject participation, or at Visit 6, whichever occurs first.

* To be performed if deemed necessary by the investigator

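### The paired change tests name no unit of analysis; run on eyes, as the plan implies, they ignore correlation between fellow eyes

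*Combined protocol and SAP*

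**What the plan says.** All references are to the combined protocol and SAP.

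- **Test.** Section 10.2.1: "For variables measured on a continuous scale, the statistical significance of within-treatment changes between time points will be investigated using paired t-tests". Ordinal variables get a Wilcoxon signed-rank test. No unit, n or method for fellow eyes is given.
- **Level.** Section 10.3: "Any statistical tests of hypotheses will employ a level of significance of alpha=0.05". Sidedness is not stated.
- **Efficacy set.** Section 10.1: "Efficacy analyses will be performed based on data from those eyes where uncomplicated cataract surgery with Vivity IOL implantation was completed".
- **Change summaries.** Section 10.2: "Summaries of the changes observed between the 1 month and 3 month post-operative visits will also be summarized". The same section gives categorical results as counts and percentages of subjects, then closes: "These summaries will be provided for all eyes completing the study".
- **Enrolment.** Section 7.1 plans 40 eyes of 20 subjects: "Both eyes of a subject must be enrolled".
- **Schedule.** Table 15.1 notes that "visits are by patient, with both eyes tested".
- **Precision.** Section 11 counts subjects: "When the sample size is 20, a two-sided 95% confidence interval for a single mean will extend 0.05 from the observed mean".

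**The concern.** A paired t-test needs independent differences. Pairing within an eye over time removes whatever is stable about that eye and that subject. It does not remove correlation between the changes in a subject's two eyes. Both eyes are tested at the same visits in the same person, so a shared shift between visits is plausible.

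The plan leaves the unit open, and its cues point to the eye. Two analysts following the text could report different p-values from the same data. The one who uses 40 eyes would understate the standard error whenever the correlation is positive. The planned 1-month to 3-month comparison is the clearest case: a real change may be small or absent there, so a false positive could be reported as a change in acuity or refraction.

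**Working it through.** **1. The plan's own figure.** Section 11 gives n = 20, SD 0.1 logMAR and a t-based 95% interval.

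Half-width = t(0.975, 19) × 0.1/√20 = 2.093 × 0.02236 = 0.047, which rounds to the stated 0.05. With n = 40 it would be 2.023 × 0.1/√40 = 0.032. The precision statement therefore counts subjects, whereas the efficacy set counts eyes.

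**2. What the change tests can act on (Table 15.1).**

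| Variable | Recorded per | Visits |
|---|---|---|
| Manifest refraction | eye | 1, 4, 5, 6 |
| Monocular distance acuity, uncorrected | eye | 1, 3, 4, 5, 6 |
| Monocular distance acuity, corrected | eye | 1, 4, 5, 6 |
| Monocular intermediate and near acuity | eye | 4, 5, 6 |
| Binocular acuities, including low contrast | subject | 6 only |
| IOLSAT, QUVID | subject | 6 only |

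Every continuous efficacy variable with more than one visit is recorded per eye. A change test has no subject-level efficacy variable to work on.

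**3. Variance.** Let σ² be the variance of one eye's change and ρ the correlation between the two eyes' changes. For 20 subjects with two eyes each:

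- true variance of the mean change = σ²(1 + ρ)/40
- expected naive variance = σ²(1 − ρ/39)/40
- ratio of true to naive SE = √[(1 + ρ)/(1 − ρ/39)]
- effective number of independent eyes = 40/(1 + ρ)

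At ρ = 0.5 the ratio is √(1.5/0.987) = 1.23, and the effective number is 40/1.5 = 26.7.

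**4. Type I error.** The documents do not give ρ, so a range is shown. Two-sided tests are assumed. The normal approximation is 2[1 − Φ(1.96/√(1 + ρ))]. The simulated column is the 40-eye t-test (39 df) with normal changes, a true change of 0 and 200,000 replicates per value.

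| ρ (assumed) | Effective eyes | True/naive SE | Approximation | Simulated |
|---|---|---|---|---|
| 0 | 40 | 1.00 | 5.0% | 4.9% |
| 0.1 | 36.4 | 1.05 | 6.2% | 6.1% |
| 0.3 | 30.8 | 1.14 | 8.6% | 8.5% |
| 0.5 | 26.7 | 1.23 | 11.0% | 11.1% |
| 0.7 | 23.5 | 1.32 | 13.3% | 13.6% |
| 0.9 | 21.1 | 1.39 | 15.5% | 16.0% |

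A separate run of 400,000 replicates gave 8.5%, 11.0%, 13.7% and 16.1% at 0.3, 0.5, 0.7 and 0.9. The signed-rank test on 40 eyes behaves the same way (10.9% at 0.5, 20,000 replicates).

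**5. Candidate corrections.**

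- The t-test on 20 subject means (19 df) rejects 4.9–5.0% at every ρ.
- Subject-clustered standard errors with 19 df reject 4.9–5.2%.
- A mixed model with only subject and eye random intercepts does not help, because both intercepts cancel in the change. In four simulated datasets with ρ = 0.7 it returned exactly the naive SE (for example 0.1357, against 0.1657 from subject means). Adding a subject-by-visit random effect returned 0.1657.

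**The case against.** The strongest case against concerns weight rather than arithmetic.

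- **The 40-eye test is inferred.** Section 10.1 says which eyes supply data, not that each eye is an independent observation; averaging two eyes also uses data from those eyes. This is fair. Yet Section 10.2 attaches the change summaries to eyes, the repeated variables are all per eye, and no clustered method appears anywhere. Without one, the eye is the natural unit.
- **No listed outcome is a change.** The primary and secondary outcomes are 3-month values or are collected only at 3 months. This stands: the affected tests are supportive. They are still planned tests with a stated alpha.
- **The correlation is unknown.** What matters is the correlation of changes, not of levels. Stable effects cancel in the change, so strong similarity between fellow eyes in level does not imply a high ρ. This stands, and a low value such as 0.1 is as compatible with the documents as a high one.
- **The null is unrealistic for some comparisons.** After cataract removal, no change from the preoperative value is hardly credible. The error rates matter mainly for comparisons among postoperative visits.
- **The signed-rank test has little to act on**, since both questionnaires are given once. This is correct, and the point rests on the t-tests.

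**Conclusion.** The concern holds. The plan prescribes significance tests without naming their unit, and its other provisions lead to up to 40 eye changes from 20 subjects being treated as independent. Under that reading the nominal 5% becomes about 6% to 16% for correlations of 0.1 to 0.9, with no inflation at 0. The assumptions are the eye-level reading, two-sided tests, normally distributed changes, two evaluable eyes in every subject, and the stated correlation range, which does not come from the documents.

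The reach is limited. The binocular primary acuities, the questionnaires and the Section 11 precision statement are at subject level and unaffected. Mean changes and percentages of eyes are not biased; only the p-values, and any intervals built on the same standard error, are wrong. It should be corrected before analysis but does not threaten the primary result.

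**What to change.** Add to Section 10.2.1:

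> For variables recorded per eye (monocular acuities, manifest refraction), the change between visits is averaged over the subject's evaluable eyes. The paired t-test or signed-rank test is applied to one value per subject, n up to 20.

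Acceptable alternatives are subject-clustered standard errors with 19 df, or a mixed model that includes a subject-by-visit random effect.

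In Section 10.2, state for each variable whether the denominator is eyes or subjects. No interval is planned for the percentage of eyes within 0.5 D of prediction. If one is added, it should also respect the pairing of eyes, for instance by resampling subjects or by GEE.

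The cost is one or two sentences and a few lines of R, with no new data or visits. P-values for the change tests will be somewhat larger and any intervals wider. As an illustration only, using Section 11's SD of 0.1 (no SD for changes is given) and ρ = 0.5, the half-width rises from 0.032 to 2.093 × 0.1 × √(1.5/40) = 0.041.

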10.3. General Statistical Considerations

The statistical analyses will be performed using R, version 4.0.3 or higher. Any statistical tests of hypotheses will employ a level of significance of alpha=0.05.

11. SAMPLE SIZE JUSTIFICATION

The distribution of axial length ≥ 24.5 mm in the older population of is $\sim 17\%$.³ As a result, recruitment for qualifying candidates will be limited due to this natural population distribution. It is expected that 20 patients (40 eyes) will provide sufficient data to characterize the clinical performance of the lens. When the sample size is 20, a two-sided 95% confidence interval for a single mean will extend 0.05 from the observed mean, assuming that the standard deviation is known to be 0.1 logMAR and the confidence interval is based on the t-statistic.

12. CONFIDENTIALITY/PUBLICATION OF THE STUDY

The existence of this Study is confidential and should not be discussed with persons outside of the Study. Results will be submitted for publication and presentation at national and/or international meetings. A manuscript will be submitted to peer-review journals for publication but there is no guarantee of acceptance.

All study data will be collected on appropriate Case Report Forms (CRFs). No protected health information will be included on the forms. CRFs will be retained in the patient's file for a minimum period of 3 years. Collected information will only be used for purposes of this study and no information will be sold to third parties. The following people will have access to your study records:

- Study Doctor and staff involved with the study
- Study Monitor or Auditor

- Sponsor Company or Research Institution
- Review boards or accrediting agencies
- Other State or Federal Regulatory Agencies

The de-identified (anonymized) data may be shared with other researchers for future analysis.

13. QUALITY COMPLAINTS AND ADVERSE EVENTS

All subjects will be monitored for adverse events over the course of the study. A place to record any adverse event is included on each case report form.

13.1. General Information

An Adverse Event (AE) is any untoward medical occurrence in a subject who is administered a study treatment regardless of whether or not the event has a causal relationship with the treatment. An AE, therefore, can be any unfavorable or unintended sign (including an abnormal laboratory finding), symptom, or disease temporally associated with the study treatment, whether or not related to the treatment. In clinical studies, an AE can include an untoward medical occurrence occurring at any time, including run-in or washout periods, even if no study treatment has been administered.

13.2. Monitoring for Adverse Events

At each visit, after the subject has had the opportunity to spontaneously mention any problems, the Investigator should inquire about AEs by asking if the patient has any problems.

13.3. Procedures for Recording and Reporting AEs and SAEs

Subsequent to signing an informed consent form, all untoward medical occurrences that occur during the course of the study must be documented on an Adverse Event Form (AEF). A separate AEF must be filled out for each event. When possible, signs and symptoms indicating a common underlying pathology should be documented as one comprehensive event. For each recorded event, the AE documentation must include the onset date, outcome, resolution date (if event is resolved), intensity (i.e., severity), any action with study treatment taken as a result of the event, and an assessment of the adverse event's relationship to the study treatment.

Nonserious Adverse Events

A nonserious AE is defined as any untoward change in a subject's medical health that does not meet serious criteria noted below (e.g., is not life-threatening, does not require hospitalization, does not prolong a current hospitalization, is not disabling, etc.). All adverse events must be reported regardless of whether or not they are related to the study treatment.

For nonserious adverse events, an AEF containing all available information will be collected on a routine basis and submitted to the Medical Monitor at the close of the study.

Serious Adverse Events

A serious adverse event (SAE) is defined as any adverse experience that meets any of the following criteria:

- Results in death.
- Is life-threatening.

NOTE: Life-threatening means that the subject was at immediate risk of death from the reaction as it occurred; i.e., it does not include a reaction which hypothetically might have caused death had it occurred in a more severe form.

- Requires inpatient hospitalization or prolongation of existing hospitalization.

NOTE: In general, hospitalization signifies that the individual remained at the hospital or emergency ward for observation and/or treatment (usually involving an overnight stay) that would not have been appropriate in the physician's office or an out-patient setting. Complications that occur during hospitalization are AEs. If a complication prolongs hospitalization or fulfills any other serious criteria, the event is serious. When in doubt as to whether "hospitalization" occurred, the event should be considered serious.

- Results in persistent or significant disability/incapacity. Disability is defined as a substantial disruption of a person's ability to conduct normal life functions.

NOTE: The term disability means a substantial disruption of a person's ability to conduct normal life functions. This definition is not intended to include experiences of relatively minor medical significance such as uncomplicated headache, nausea, vomiting, diarrhea, influenza, or accidental trauma (e.g., sprained ankle) which may interfere or prevent everyday life functions but do not constitute a substantial disruption.

- Is an important medical event. An important medical event is an event that may not result in death, be life-threatening, or require hospitalization but may be considered an SAE when, based upon appropriate medical judgment, it may jeopardize the subject and may require medical or surgical intervention to prevent one of the outcomes listed in the definitions for SAEs. Examples of such medical events include allergic bronchospasm requiring intensive treatment in an emergency room or at home, blood dyscrasias or convulsions that do not result in subject hospitalization, or the development of drug dependency or drug abuse.

All available information on a serious adverse event(s) and any other associated AE, if applicable, must be forwarded to the study coordinator for forwarding to the Medical Monitor immediately (i.e., within one working day of the Investigator's or site's knowledge of the event) as follows:

- In studies utilizing EDC (electronic data capture), all available information for the SAE and any associated AE(s) must be entered immediately into the EDC system.
- Additional information for any applicable event is to be reported as soon as it becomes available.

In addition to the reporting of serious adverse events to the study Medical Monitor, the SAE must be reported to the IRB / IEC according to their requirements.

The investigator must document all adverse device events (serious and nonserious but related) and all serious adverse events (related and unrelated) on the Adverse Device Effect and Serious Adverse Event Form. Any device quality complaints will also be documented.

- **Both the Quality Complaint Form and the Adverse Device Effect and Serious Adverse Event Form must be e-mailed immediately to the study coordinator ([name]) at [contact].**
- **Additional relevant information is to be reported as soon as it becomes available.**

Study coordinator contact information is provided below.

Table 13.3.-1:
Contact Information for Study

Study Staff	Business Phone	e-mail	24-hour Office Phone

12.3.1 Intensity and Causality Assessments

For every adverse event and quality complaint, the investigator must assess the causality as Related or Not Related to the medical device under investigation. An assessment of causality will also be performed by the Medical Monitor utilizing the same definitions, as shown below:

Causality

Related

An adverse event or quality complaint classified as related may be either definitely related or possibly related where a direct cause and effect relationship with the medical device has not been demonstrated, but there is a reasonable possibility that the adverse

event or quality complaint was caused by the medical device.

Not Related An adverse event or quality complaint classified as not related may either be definitely unrelated or simply unlikely to be related (i.e., there are other more likely causes for the adverse event or quality complaint).

Where appropriate, the investigator must assess the intensity (severity) of the adverse event as mild, moderate, or severe based on medical judgment with consideration of any subjective symptom(s), as defined below:

Intensity (Severity)

Mild	An adverse event is mild if the subject is aware of but can easily tolerate the sign or symptom.
Moderate	An adverse event is moderate if the sign or symptom results in discomfort significant enough to cause interference with the subject's usual activities.
Severe	An adverse event is severe if the sign or symptom is incapacitating and results in the subject's inability to work or engage in their usual activities.

The investigator must document any action taken (i.e., medication, intervention, or treatment plan) and outcome of the adverse event or quality complaint when applicable.

13.4. Follow-Up of Adverse Events and Quality Complaints

The investigator is responsible for adequate and safe medical care of subjects during the study and for ensuring that appropriate medical care and relevant follow-up procedures are maintained after the study. Any additional data from these follow-up procedures must be documented and available to the study coordinator who, with the Medical Monitor, will determine when the data need to be documented on the CRFs.

